### **3.6.2.6. Major Protocol Deviations**

See Section 2.6.2.6 for details.

## **3.6.3. Safety Analysis**

See Section 2.6.3 for details.

### **3.6.3.1. Solicited Adverse Reactions**

See Section 2.6.3.1 for details.

#### **3.6.3.1.1 Overview of Solicited ARs**

See Section 2.6.3.1.1 for details.

#### **3.6.3.1.2 Solicited ARs by Toxicity Grade**

See Section 2.6.3.1.2 for details.

#### **3.6.3.1.3 Solicited ARs by Onset Day**

See Section 2.6.3.1.3 for details.

### **3.6.3.1.4 Characteristics of Solicited ARs**

See Section 2.6.3.1.4 for details.

### **3.6.3.1.5 Other solicited ARs summaries**

See Section 2.6.3.1.5 for details.

## **3.6.3.2. Unsolicited Treatment-Emergent Adverse Events**

See Section 2.6.3.2 for details.

Unsolicited AEs will be coded according to Medical Dictionary for Regulatory Activities (MedDRA) version 26.0 or higher and presented by MedDRA system organ class (SOC) and preferred term (PT).

SOC will be displayed in an internationally agreed order. PT will be displayed in descending order of frequency of the combined mRNA-1083 (CC1).

### **3.6.3.2.1 Overview of Unsolicited TEAEs**

See Section 2.6.3.2.1 for details.

### **3.6.3.2.2 TEAEs by System Organ Class and Preferred Term**

See Section 2.6.3.2.2 for details.

### **3.6.3.2.3 TEAEs by Preferred Term**

Tables of all unsolicited TEAEs will be provided by PT sorted in a descending order starting with the frequency of the combined mRNA-1083 (CC1).

### **3.6.3.2.4 TEAEs by Severity**

See Section 2.6.3.2.4 for details.

## **3.6.3.3. Death**

See Section 2.6.3.3 for details.

### **3.6.3.4. Vital Signs**

See Section 2.6.3.5 for details.

### **3.6.3.5. Pregnancy Testing**

See Section 2.6.3.6 for details.

### **3.6.3.6. Other Safety Data**

#### **3.6.3.6.1 Safety Telephone Calls**

See Section 2.6.3.7.1 for details.

#### **3.6.3.6.2 Assessment for Respiratory Viral Infection**

For Part 2, all participants will provide nasal swab samples before the injection on Day 1 for assessment of infection with respiratory pathogens, including influenza viruses and SARS-CoV-2, as influenza or COVID-19 symptoms may confound reactogenicity assessments.

#### **3.6.3.6.3 Physical examination**

See Section 2.6.3.7.3 for details.

#### **3.6.3.6.4 Electrocardiograms**

See Section 2.6.3.7.4 for details.

### **3.6.4. Immunogenicity Analysis**

The primary analysis population for immunogenicity will be the PP Set. Planned timepoints for all immunogenicity assessments are provided in the SoA available in Appendix A.

For Part 2, the following analytes will be measured:

- Influenza: Serum antibody level as measured by HAI assay and potentially serum neutralizing antibody (nAb) level as measured by microneutralization assay.

- SARS-CoV-2: Serum nAb titers as measured by pseudovirus neutralization assay (PsVNA) assay and potentially serum binding antibody titers by enzyme-linked immunosorbent assay or multiplex assay specific to the SARS-CoV-2 proteins.

See section 2.6.4 for primary, secondary and exploratory endpoints calculation methods.

### 3.6.4.1. Primary Immunogenicity Endpoints

- GMT and GMFR at Day 29 compared to Day 1 by HAI assay for influenza and by PsVNA for SARS-CoV-2
- Influenza: Percentage of participants with seroconversion, defined as a Day 29 titer  $\geq$  [redacted] if Baseline is **CCI** or a 4-fold or greater rise if Baseline is **CCI** in anti-HA antibodies measured by HAI assay
- SARS-CoV-2: Percentage of participants with seroresponse, defined as a Day 29 titer  $\geq$  4-fold if Baseline is  $\geq$  LLOQ or  $\geq 4 \times$  LLOQ if Baseline titer is  $<$  LLOQ in nAb titers measured by PsVNA

For the primary immunogenicity endpoints, descriptive summaries statistics, including median, Q1, Q3, minimum, and maximum will be provided at Day 29 for the antibody titer values by treatment arm (available in Section 3.6.1) for the influenza and SARS-CoV-2 endpoints:

- GMT with corresponding 2-sided 95% CI
- GMFR of specific antibody titers with the corresponding 2-sided 95% CI at Day 29 over pre-injection Baseline at Day 1,

In addition, the following analysis statistics will be provided by treatment arm at Day 29 for the influenza and SARS-CoV-2 endpoints:

- Within treatment group, model-based GMT with the corresponding 95% CI,
- Between treatment group, pair-wise geometric mean ratios (GMR) with the corresponding 95% CI

The model-based GMT will be estimated by the geometric least square mean (GLSM) from the ANCOVA model for each treatment group and corresponding 2-sided 95% CI will be provided.

In the ANCOVA model, the log-transformed antibody titer at Day 29 is treated as a dependent variable, with the treatment group as an explanatory variable and covariates listed in Table 14 for different assays and subgroups.

**Table 14 Covariates Included in Different ANCOVA Models (Part 2)**

Assay	Subgroup	Covariate(s)
PsVNA	Overall	Log-transformed baseline antibody value, Influenza Vaccine Status Since Sept 2023 (IRT)
	Overall	Log-transformed baseline antibody value
	Covid Vaccine Status Since Sept 2023: Received	Log-transformed baseline antibody value
	Covid Vaccine Status Since Sept 2023: Not Received	Log-transformed baseline antibody value
	Baseline SARS-CoV2 Status: Positive	Log-transformed baseline antibody value
	Baseline SARS-CoV2 Status: Negative	Log-transformed baseline antibody value
HAI	Overall	Log-transformed baseline antibody value, Influenza Vaccine Status Since Sept 2023 (IRT)
	Overall	Log-transformed baseline antibody value, Influenza Vaccine Status Since Sept 2023 (EDC)
	Influenza Vaccine Status Since Sept 2023 (EDC): Received	Log-transformed baseline antibody value
	Influenza Vaccine Status Since Sept 2023 (EDC): Not Received	Log-transformed baseline antibody value

For each pair of between-group comparison specified in Table 15, the GMR between the two treatment groups in each pair will be estimated from the ANCOVA model, with its 2-sided 95% CI provided accordingly.

Seroconversion rate (SCR) for influenza from Baseline will be summarized at Day 29 with its 2-sided 95% CI using the Clopper-Pearson method for participants in the groups receiving mRNA-1083, mRNA-1010 or Fluarix.

- SCR at Day 29 is defined as the percentage of participants with a Day 29 titer **CCI** if Baseline is **CCI** or a 4-fold or greater rise if Baseline is **CCI** in anti-HA antibodies measured by HAI assay

Seroresponse rate (SRR) for SARS-CoV-2 from Baseline will be summarized at Day 29 with its 2-sided 95% CI using the Clopper-Pearson method for participants in the groups receiving mRNA-1083, mRNA-1283.815 or mRNA-1273.815.

- SRR at Day 29 is defined as the proportion of participants with a Day 29 titer  $\geq$  4-fold if Baseline is  $\geq$  LLOQ or  $\geq 4 \times$  LLOQ if Baseline titer is  $<$  LLOQ in nAb titers measured by PsVNA.

Additional comparisons or analysis statistics will be provided by treatment arm at Day 29 for the influenza and SARS-CoV-2 endpoints. For each pair of between-group comparison specified in Table 15, the difference of seroresponse/seroconversion rate (SRR/SCR) between the two treatment groups in each pair will be provided, with its 2-sided 95% CI estimated using Miettinen-Nurminen method.

SCR, SRR, GM levels, GMFR and GMR will be plotted at Day 29: Reverse Cumulative Distribution Function for each specific strain of influenza and SARS-CoV-2 will be provided, as well as box plot and bar plot for GMT and GMFR, and bar plot for GMR, SCR and SRR.

Listing presenting the antibody level, for each specific strain of influenza and SARS-CoV-2 will be provided. The ratio of post-Baseline/Baseline, LLOQ and ULOQ will be presented as well.

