**Table 8: Probability of AEs Based on Sample Size(Part 1)**

n	True AE Rate	Probability of 0 AE	Probability of at Least 1 AE Observed
50	2.0%	36.4%	63.6%
50	3.0%	21.8%	78.2%
50	4.0%	13.0%	87.0%
50	5.0%	7.7%	92.3%

### 9.3.2. Part 2

Approximately, 520 participants will be enrolled at an evenly allocated ratio across the 13 treatment arms in Part 2 for adults  $\geq 18$  to  $< 50$  years of age, with 40 participants planned for each arm. Approximately 40 participants in each group receiving an investigational injection have approximately 80.5% (or 87.1%) probability to observe at least 1 participant with an AE given the true underlying incidence rate of AE is 4% (or 5%).

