## SUMMARY OF MAJOR CHANGES IN SAP VERSION

SAP Version	Section # and Name	Description of Change
V2.0	5.3 Per Protocol (PP) Set	Clarified existing language for conditions/medications that affect the immune response.
V2.0	6.1 General Considerations	Clarified that all subgroups are based on eCRF entries unless otherwise stated. Added definition for Baseline SARS-CoV-2 Status and added this Baseline SARS-CoV-2 Status to Table 5, as a subgrouping factor to be used in table summaries.
V2.0	6.2.2 Demographics and Baseline Characteristics	Added 3 categorical baseline variables: Baseline SARS-CoV-2 RT-PCR Results, Elecsys Anti-SARS-CoV-2 Results, and Baseline SARS-CoV-2 Status.
V2.0	6.3.2 Unsolicited Treatment-Emergent Adverse Events	Updated to reflect only Solicited ARs that meet SAE criteria are recorded on the Reactogenicity eCRF.
V2.0	6.4.2 Immunogenicity Analysis	Updated wording in 6.4.2.2 Analytical summaries, and added a new Table 6 to clarify the covariates used in the ANCOVA analyses. Renumbered later tables and added clarifying language to Table 7. Removed bar-plot of ANCOVA-based GMT.
V3.0	6.2.4 Prior and Concomitant Medications	“Antipyretic or analgesic medication within 28 days postinjection” item removed
V3.0	6.4.2.1. Analysis of Secondary Immunogenicity Endpoints	For GMFR, values below LLOQ imputed to LLOQ
V3.0	6.4.2.2 Analytical summaries	Added D181 GMT/GMR; added figure for D181 GMFR, SCR, SRR, and GMR
V3.0	6.5.1.2 SARS-CoV-2 Infection	Asymptomatic SARS CoV 2 infection language removed
V3.0	Appendix H TEAE of Specifical Interest by SMQ	SMQ table updated
V4.0	Global update	Part 2 added to the SAP per protocol amendment 1 dated 16-Jan-2024 and protocol amendment 2 dated 14 Mar 2024
V5.0	3.6.4.1. Primary Immunogenicity Endpoints	Updated the “Covariate(s)” column in Table 14, by adding “Log-transformed baseline antibody value” for all rows.

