### **3.3.4. Randomization**

Participants will be randomized (in equal allocation ratio) into the investigational treatment arms, stratified by influenza vaccine status in the most recent influenza season (received or not received since Sept 2023).

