**Table 13 Definition for Subgroups (Part 2)**

Subgroup Variable	Categories
Influenza Vaccine Status Since Sept 2023	Received Not Received
Covid Vaccine Status Since Sept 2023	Received Not Received
Baseline SARS-CoV-2 Status	Positive Negative

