#### **3.6.2.2. Demographics and Baseline Characteristics**

Descriptive statistics for age, weight, height, and BMI are described in Section 2.6.2.2.

The number and percentage of participants will be provided for the following categorical variables:

- Sex (Male, Female)
- Race (White, Black or African American, Asian, American Indian or Alaska Native, Native Hawaiian or Other Pacific Islander, Multiracial, Other, Not Reported, Unknown)
- Ethnicity (Hispanic or Latino, Not Hispanic or Latino, Not Reported, Unknown)
- Influenza vaccine status in the most recent influenza season (received or not received since Sept 2023) per eCRF
- Covid vaccine status (received or not received since Sept 2023) per eCRF
- Childbearing Potential for female participants (Yes/No) and reason if “No”
- Baseline SARS-CoV-2 RT-PCR Results (positive, negative, or missing)
- Baseline Elecsys Anti-SARS-CoV2 Results (positive, negative, or missing)

- Baseline SARS-CoV-2 Status (positive, negative, or missing)

The summaries will be provided separately for all analysis sets (except Randomization Set and Solicited Safety Set) defined in the Section 3.5. The number and percentage of participants randomized by country and site will be provided as well.

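### Part 2: neither Overall PsVNA model adjusts for COVID-19 vaccination since September 2023, although the trial records it and uses it as a PsVNA subgroup; one added covariate would give a small gain in precision.

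*SAP*

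**What the plan says.** Day 29 response by PsVNA is a primary endpoint of Part 2 (SAP 3.2.1). Randomization has a single factor: it is "stratified by influenza vaccine status in the most recent influenza season (received or not received since Sept 2023") (SAP 3.3.4).

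The Day 29 GMRs come from the ANCOVA models in SAP Table 14. Its Overall rows are:

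| Assay | Overall row | Covariates besides treatment |
|---|---|---|
| PsVNA | first | "Log-transformed baseline antibody value, Influenza Vaccine Status Since Sept 2023 (IRT") |
| PsVNA | second | "Log-transformed baseline antibody value" |
| HAI | first | log baseline titer, influenza vaccine status (IRT) |
| HAI | second | log baseline titer, influenza vaccine status (EDC) |

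The table does not say which Overall row is the main one.

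COVID-19 vaccination since September 2023 appears elsewhere. SAP 3.6.2.2 tabulates "Covid vaccine status (received or not received since Sept 2023) per eCRF", and SAP Table 13 lists "Covid Vaccine Status Since Sept 2023" as a subgroup variable. Table 14 has a separate PsVNA model for each level, for example "Covid Vaccine Status Since Sept 2023: Received", each adjusted for log baseline titer.

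Protocol 5.2.1 requires at least 2 COVID-19 vaccine doses, the last at least 90 days before Day 1. Protocol Table 4 shows that the Part 2 SARS-CoV-2 components encode XBB.1.5, and protocol Section 2 records that an XBB.1.5 vaccine was approved in September 2023.

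**The concern.** Eligibility sets a minimum number of doses and a minimum gap, but it does not fix which antigen was last received. Participants vaccinated since September 2023 may already have met the XBB.1.5 antigen; the others most likely have not met it by vaccination. Two people with the same Day 1 titer could therefore respond differently on Day 29. To that extent the status is a prognostic covariate beyond baseline titer.

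Because the status is not a stratum, its share in each arm is left to chance. With 40 per arm, two arms can differ noticeably. An unadjusted difference moves the GMR of that pair up or down. What is at stake is the precision and reading of single comparisons when mRNA-1083 dose levels and compositions are set against mRNA-1283.815 and mRNA-1273.815.

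The second Overall PsVNA row is the natural place for the covariate. It drops the influenza stratum and puts no other vaccination variable in its place.

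**Working it through.** **Inputs from the documents.** "Approximately, 520 participants will be enrolled at an evenly allocated ratio across the 13 treatment arms in Part 2", that is 520/13 = 40 per arm (protocol 9.3.2). SAP Table 15 compares 8 mRNA-1083 arms with 2 comparators, and mRNA-1283.815 with mRNA-1273.815: 8 x 2 + 1 = 17 SARS-CoV-2 pairs.

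**The plan's own figure.** The only Part 2 sample-size figures are probabilities of seeing at least one AE with n = 40. The formula 1 - (1 - p)^40 gives 55.4%, 70.4%, 80.5% and 87.1% at 2%, 3%, 4% and 5%, as in protocol Table 9. No figure is given for the PsVNA comparisons.

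**Assumptions.** The documents give no vaccinated share, titer SD or effect size. I take:
- share vaccinated since September 2023: p = 0.35 (range 0.20 to 0.50);
- fold difference in Day 29 titer given baseline titer: r = 1.3 to 1.5, with r = 1 if baseline titer carries everything;
- residual SD: s = 0.35 to 0.5 log10.

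**Step 1: chance imbalance.** For one pair, the SD of the difference in shares is sqrt(2p(1-p)/40) = sqrt(2 x 0.2275/40) = 0.107, or 10.7 points. From the exact binomial distribution, the median absolute difference is 3/40 = 7.5 points, and a given pair reaches 20 points about 8% of the time. Simulating all 17 pairs with independent Binomial(40, p) arms gives a median largest difference of 20 points. The probability that at least one pair reaches 20 points is:

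| p | P(at least one of 17 pairs at 20 points or more) |
|---|---|
| 0.20 | about 0.32 |
| 0.35 | 0.55 |
| 0.50 | 0.61 |

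**Step 2: shift in a GMR.** The shift is r^d - 1, where d is the imbalance as a proportion.

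| Imbalance | r = 1.3 | r = 1.5 |
|---|---|---|
| typical pair, d = 0.075 | 1.3^0.075 - 1 = 2.0% | 1.5^0.075 - 1 = 3.1% |
| worst of 17, d = 0.20 | 1.3^0.20 - 1 = 5.4% | 1.5^0.20 - 1 = 8.4% |

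**Step 3: gain in precision.** Leaving the covariate out adds p(1-p)(log10 r)^2 to the residual variance. Including it narrows a confidence interval, on the log scale, by 1 - sqrt(s^2 / (s^2 + p(1-p)(log10 r)^2)).
- r = 1.3: the added variance is 0.2275 x 0.1139^2 = 0.00295, and the narrowing is 0.6% (s = 0.5) to 1.2% (s = 0.35).
- r = 1.5: the added variance is 0.2275 x 0.1761^2 = 0.00705, and the narrowing is 1.4% to 2.8%.
- r = 1: no gain.

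**Step 4: validity.** A separate ANCOVA simulation used 10 arms of 40, with assumed baseline SD 1.8 log2, residual SD 1.3 log2, slope 0.5 and baseline shift 1.5 log2 in the vaccinated. With or without the extra covariate, the mean log2 GMR stayed within 0.02 of the true 0 and coverage was about 94-96%. The 95% interval half-width was a factor of about 1.49 to 1.52 without the covariate and about 1.49 with it. The largest gain came at a residual 2-fold effect with 50% vaccinated.

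**The case against.** The strongest case is that the plan already covers most of this.

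- **Baseline titer is in every PsVNA row.** SAP V5.0 added it throughout Table 14, and it takes up whatever part of earlier vaccination or infection shows on Day 1. This stands, and it is why the gain is small. A reader might infer that influenza vaccination was put in place of the relevant background variable. The documents do not support that: only one of the two Overall rows carries influenza status, it is there as the randomization stratum, and both rows carry the baseline titer.
- **Separate models by COVID-19 vaccine status are planned.** Imbalance in the status cannot disturb those within-level GMRs, and the baseline table will show any imbalance. A reader might therefore infer too much by calling the SARS-CoV-2 comparisons unprotected. Still, the subgroup models split arms of 40, and no combined estimate adjusted for this status is planned.
- **Randomization balances the status in expectation.** It is unstratified, not unbalanced by design. The imbalance is noise that the confidence intervals already reflect, and no formal hypothesis test, margin or power calculation rests on these GMRs. This stands.
- **The 20-point figure is a worst case, and zero correlation is assumed.** If COVID-19 and influenza vaccination go together, the existing stratum already helps. With exact stratification and an assumed 40% influenza-vaccinated, the probability of any pair reaching 20 points falls from 0.55 to 0.36 or 0.26 at correlations of 0.5 or 0.6. The documents give no correlation.
- **The omission looks consistent.** SAP Table 6 also leaves prior bivalent COVID-19 vaccination out of the Part 1 Overall PsVNA models and uses it as a subgroup. The two HAI rows differ only in the data source for the same stratum, so a COVID-19 covariate in PsVNA would not be an exact parallel.

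What remains is that a recorded and plausibly prognostic variable, which the SAP itself treats as relevant to PsVNA, is missing from both Overall estimates.

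**Conclusion.** The point holds as a cheap improvement in precision, not as a flaw in validity. COVID-19 vaccination since September 2023 is not a stratum and is in neither Overall PsVNA model. The XBB.1.5 match gives a reason to expect some effect beyond baseline titer, but the documents do not show one.

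If 35% were vaccinated and the residual effect is 1.3- to 1.5-fold, a typical pair shifts by 2-3%, the worst of 17 by 5-8%, and adjustment narrows intervals by about 0.6-3%. The gain is nil if baseline titer carries the whole effect, and imbalances will be smaller if the two vaccinations are correlated. Share, fold effect and SD are all assumptions.

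Nothing here supports a claim of systematic bias or inflated type I error.

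**What to change.** In SAP Table 14, either add Covid Vaccine Status Since Sept 2023 (eCRF) to the second Overall PsVNA row, or keep that row and add a further Overall row with log baseline antibody value plus this status. Leave the row with the IRT stratum unchanged. It would also help to state which Overall row is the main one.

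The cost is one model degree of freedom and a small amount of extra analysis on data already collected. The randomization need not be touched: a second stratum would change the study design and so need a formal protocol amendment (protocol 10.1.5), which a gain of this size does not justify.

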**Table 15 Between-group Immunogenicity comparisons (Part 2)**

		Influenza Comparisons									
		mRNA-1010. cc1 μg	mRNA-1010. cc1 μg	mRNA-1083. cc1 μg							
Control Group	Fluarix	X	X	X	X	X	X	X	X	X	X
	mRNA-1010. cc1 μg	NA	X	X	X	X	X	X	X	X	X
	mRNA-1010. cc1 μg	NA	NA	X	X	X	X	X	X	X	X
SARS-CoV-2 Comparisons											
		Treatment Arm									
		mRNA-1283.815. cc1 μg	mRNA-1083. cc1 μg								
Control Group	mRNA-1273.815. cc1 μg	X	X	X	X	X	X	X	X	X	X
	mRNA-1283.815. cc1 μg	NA	X	X	X	X	X	X	X	X	X

### 3.6.4.2. Secondary Immunogenicity Endpoints

- GMT and GMFR at all evaluable time points compared to Day 1 by HAI for influenza and PsVNA for SARS-CoV-2
- Influenza: Percentage of participants with seroconversion
- SARS-CoV-2: Percentage of participants with seroresponse

For the secondary immunogenicity endpoints, descriptive summaries statistics, including median, Q1, Q3, minimum, and maximum will be provided for each timepoints for the antibody titer values by treatment arm (available in Section 3.6.1) for the influenza and SARS-CoV-2 endpoints:

- GMT with corresponding 2-sided 95% CI
- GMFR of specific antibody titers with the corresponding 2-sided 95% CI at each post-baseline timepoint Day 29 over pre-injection Baseline at Day 1

Additional descriptions will be provided by treatment arm (available in Section 3.6.1) for the following influenza and SARS-CoV-2 endpoints:

- Percentages of participants with seroconversion (influenza) and seroresponse (SARS-CoV-2) with the corresponding 2-sided 95% CI at each post-Baseline time point,
- Percentages of participants with a GMFR results  $\geq 2$ , and  $\geq 4$  with the corresponding 2-sided 95% CI at each post-Baseline time point.

Reverse Cumulative Distribution Function for each specific strain of influenza and SARS-CoV-2 will be provided, as well as box plot and bar plot for GMT and GMFR, and bar plot for GMR, SCR and SRR at all evaluable timepoints.

### 3.6.4.3. Exploratory Immunogenicity Endpoints

The below exploratory analyses of immunogenicity may be performed:

- GMT and GMFR at all evaluable time points compared to Day 1 by HAI for influenza and PsVNA for SARS-CoV-2
- Influenza: Percentage of participants with seroconversion, as defined above
- SARS-CoV-2: Percentage of participants with seroresponse, as defined above

- GMT and GMFR at all evaluable time points compared to Day 1 by alternative methods, including, but not limited to: microneutralization assay for influenza or ligand-binding assay for SARS-CoV-2
- Frequency, specificities, or other endpoints to be determined for the further characterization of immune responses

### **3.6.5. Other Exploratory Endpoints**

Transcriptomic and genomic samples will be part of the optional biomarker assessment. Exploratory assessments may include assessment of biomarkers for safety, reactogenicity, and inflammation. Serologic markers of disease severity, immune response to SARS-CoV-2 or influenza, reverse transcription polymerase chain reaction (RT-PCR) of nasal swab samples, genetic sequences of SARS-CoV-2 or influenza strains isolated from participants' samples, and genomic and transcriptomic samples may also be evaluated. Analyses and reporting of these endpoints will be covered in a separate analysis plan if applicable.

